8.3.6.4. Other Safety Analyses

Subject demographics, medical history, prior and concomitant medications, vital sign measurements, laboratory values, physical examination assessments, will be summarized by treatment group using descriptive statistics.

For continuous variables, these summaries will include sample size, mean, median, standard deviation, minimum, and maximum. For categorical variables, the summaries will include frequencies and corresponding percentages.

For SAEs, AEs leading to permanent IP withdrawal and AEs of special interest, the number and percentage of subjects, total number of events and incidence density will be presented by treatment group and overall at the SOC and Preferred Term (PT) level. Relative Risk and its 95% CI may also be presented on a targeted basis. The time to first occurrence of specific events will be summarized.

All cause mortality will be summarized by treatment group and analyzed using a Cox PH model similarly as the-primary endpoint.

All events sent to CEC (including TIAs) will be summarized.

Pancreatitis events will be adjudicated by the independent Pancreatitis Adjudication Committee. The information for investigator reported pancreatitis events and its adjudication results will be summarized.

Further analysis details will be provided in the RAP.

8.3.6.5. Value Evidence and Outcomes Analyses

TRIM-D total score and score for each domain will be summarized descriptively by treatment group and scheduled visit. Score changes from baseline will be compared between treatments for each visit by an ANCOVA model.

For EQ-5D, subjects' responses at each visit for the 5 domains will be summarized categorically by treatment group, together with the summary of utility score at each visit and change from baseline by treatment group. Change from baseline will be compared between treatment groups for each visit by an ANCOVA model.

For study specific PRO questions, responses will be summarized descriptively by treatment group and scheduled visit.

Healthcare resource use will be summarized by treatment group and visit.

Further analysis details will be provided in the RAP.

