2. OBJECTIVES AND ENDPOINTS

| Objectives | Endpoints |
|--|--|
| Primary | |
| To assess the effect of albiglutide with respect to MACE when added to glycaemic standard of care versus standard of care alone | 
Time to first occurrence of MACE (cardiovascular death, myocardial infarction, or stroke)
 
The primary analysis will be non-inferiority. If the pre-specified non-inferiority criterion is met then superiority testing will be performed¹
 |
| Secondary | |
| To supplement the primary objective by further characterization of the effects of albiglutide on cardiovascular outcomes | 
 • Time to first occurrence of the following: 
 ▪ MACE or urgent revascularisation for unstable angina ▪ The individual components of the primary endpoint ▪ Cardiovascular death or hospitalization due to heart failure |
| To evaluate the effects of albiglutide on metabolic management of type 2 diabetes | 
 • Time to initiation of insulin of more than 3 months duration for those subjects not treated with insulin at study start • Time to initiation of prandial insulin in those subjects on basal insulin at study start • The proportion of subjects achieving glycaemic control (HbA1c \leq 7.0% at final assessment) with no severe hypoglycaemic incidents and weight gain $<$5% of body weight • The time to first occurrence of a clinically important microvascular event (see Section 6.2.4) • Change in HbA1c • Change in body weight • Patient reported outcomes from TRIM-D/EQ5D |
| To evaluate the safety of albiglutide | 
 • All cause mortality • Non-fatal SAEs • AEs leading to discontinuation of investigational product • AE of special interest (see Section 6.2.3) • Change in eGFR calculated using MDRD formula • Change in blood pressure and heart rate |
| Exploratory | |
| To evaluate patient reported experience of diabetes treatment | 
 • Patient reported outcomes from study specific questionnaire |

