This study is designed with minimal intervention above normal clinical care of subjects with type 2 diabetes, whilst allowing thorough evaluation of cardiovascular and other events of special interest (Section 6.2.3), thus investigating the safety of albiglutide in the typical clinical situation. Sites will employ pre-screening to assess potential subjects for study entry. Screening and randomisation can then occur at the same visit or in close proximity depending on scheduling. Contact with subjects will be every four months

after the randomisation visit. HbA1c will be measured at 4 month clinic visits. Serum creatinine and liver function tests (LFTs) will be measured and a targeted physical assessment performed at 8 month clinic visits (Table 1).

The study will continue until it is projected that at least 611 adjudicated MACE events will have occurred while requiring that the projected median duration of subject follow-up be at least 1.5 years. The maximum duration of the study for an individual participant is dependent both on the time taken for recruitment and the MACE event rate, and was originally estimated to be between 3 and 5 years. If the observed rate for MACE is 2.0% or 3.0%, the mean follow-up will be 3.2 or 2.2 years, respectively. If the observed rate for MACE is sufficiently high such that the median subject follow-up would be less than 1.5 years then the study will continue until it is projected that the median follow-up is at least 1.5 years. In this scenario, the maximum duration of the study for an individual participant would be less than the 3 to 5 years originally estimated.

An Executive Committee will be the main decision-making body for the study, in collaboration with the Sponsor (GSK). It is charged with the overall scientific, professional and operational conduct of the study. Amongst other roles pre-specified in its Charter, the Executive Committee will ensure proper study conduct and conformance to the protocol, consider and agree changes to the protocol based on emerging scientific and/or clinical advances (e.g., new emerging data with other GLP-1 receptor agonists), advise on the selection of study sites and assist in subject recruitment strategies.

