6. STUDY ASSESSMENTS AND PROCEDURES

The schedule of study assessments is shown in [Table 1](#) and [Table 2](#). Detailed procedures for each assessment are provided in the SRM.

Table 1 Time and Events Table

| Procedures ^{1,2} | Screening ³ | Randomization ³ /Baseline (can be same day as Screening Visit) | Study Drug Check Phone Call (4-6 wks post rand.) | Clinic Visit Month 4 ± 18 days then every 4 months ± 18 days throughout the study | Unscheduled dose adjustment visit (if warranted) | Final study clinic visit ⁴ (or early withdrawal) | Follow up Phone Call 5 ± 1 weeks after last IP dose |
|--|------------------------|--|--|---|---|--|--|
| Written informed consent | X | | | | | | |
| Review of Inc/excl criteria | X | X | | | | | |
| Demography & directed medical history | X | | | | | | |
| Assessment of MACE and micro-vascular events | | | | X | | X | |
| HbA1c | X ⁵ | | | X | | X | |
| Serum creatinine (eGFR) | X ⁵ | | | X (alternate visits) ² | | X | |
| Liver Function Tests (LFTs) ⁶ | | X | | X (alternate visits) ² | | X | |
| Record available information on most recent lipid assessment ⁷ | | X | | X (annually) | | X | |
| Genetic sampling ⁸ | | X | | | | | |
| Patient reported outcomes questionnaires ⁹ | | X ¹⁰ | | X (alternate visits) ² | | X | |
| Key concomitant non-diabetes medication | | X | | X | | X | X |
| Diabetes medication | | X | | X | | X | X |
| Study drug reminder | | | X | X | X | | |
| Physical examination ¹¹ | | X | | X (alternate visits) ² | | X | |
| SAEs, AEs of special interest, AEs leading to IP discontinuation | | X | X | X | X | X | X |
| Pregnancy test ¹² | X | X | | | | | |
| Study drug dispense/compliance ¹³ | | X | | X | X | X | |

- Subjects who discontinue investigational product should be handled as described in Section 4.4 and Section 4.5 and in Table 2.
- Assessments at month 8, 16, 24 etc. will include patient reported outcomes questionnaires, serum creatinine (eGFR), LFTs and physical examination. Those at months 4, 12, 20 etc do not.
- Screening and Randomisation can occur at the same visit if all eligibility information is available. If Screening and Randomisation occur at the same visit assessments should not be duplicated.
- Once it is projected that the target number of MACE events will have been collected and that the projected median duration of subject follow-up is at least 1.5 years, a 3 month window will be defined for conducting the final, face to face visit.

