6.3. Value Evidence and Outcomes

6.3.1. Value Evidence and Outcomes Assessments

6.3.1.1. Treatment Related Impact Measure – Diabetes (TRIM-D)

In order to evaluate satisfaction with treatment and to compare satisfaction across treatment groups, the TRIM-D questionnaire will be self administered by all subjects at baseline (except for subjects whose diabetes is treated by diet and exercise alone) and all subjects at each 8 month visit (and, to the extent possible, at the time of study completion or withdrawal from the study).

The TRIM-D, developed in 2009, is a 28-item treatment satisfaction measure scored to produce 5 sub-scale scores (Treatment Burden, Daily Life, Diabetes Management, Psychological Health, and Compliance) as well as a total score. It is available in a wide range of translations.

The TRIM-D development, in accordance with the principles of the Food and Drug Administration Patient Reported Outcome Guidance document, was based on findings from the published literature including content from already-existing treatment satisfaction measures as well as significant input from subjects with type 1 and with type 2 diabetes and from expert diabetes clinicians. The TRIM-D has been evaluated in a sample of 507 subjects (74% with type 2 diabetes) and has been shown to have acceptable reliability and validity [Brod, 2009a]. Its responsiveness was also evaluated in a sample of 242 subjects (71% with type 2 diabetes) and found to be acceptable [Brod, 2009b]. Some preliminary work has been done on estimating its minimal important difference but this needs further exploration [Brod, 2009b].

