8.3.5. Multiplicity Controls

If non-inferiority is established for the primary endpoint, the data will be used to test for evidence of superiority. This approach is a closed testing procedure, and therefore, no adjustment for multiplicity is required [Hung, 2009].

Other Secondary Endpoints and Subgroup Analysis

The following secondary endpoints will provide supportive evidence for cardiovascular safety and metabolic efficacy and will not use any multiplicity adjustment procedure. Results will be presented with confidence interval and nominal p-values:

Components of primary endpoint (MACE = cardiovascular death, MI, stroke)

MACE + urgent revascularisation for unstable angina

Cardiovascular death or hospitalisation for heart failure

Time to initiation of insulin of more than 3 months duration for those subjects not treated with insulin at study start

Time to initiation of prandial insulin in those subjects treated with basal insulin at study start.

The proportion of subjects achieving glycaemic control ($\text{HbA1c} \leq 7.0\%$ at final assessment) with no severe hypoglycaemic incidents and weight gain $<5\%$ of body weight

Mean HbA1c at scheduled visits and change from baseline

Mean body weight at scheduled visits and change from baseline

Mean eGFR at scheduled visits and change from baseline

Composite microvascular endpoint

To examine the degree of consistency of the overall treatment effect in terms of important prognostic factors, subgroup analyses of the primary outcomes will be performed based on subject demographics and baseline characteristics. These exploratory subgroup analyses will not be adjusted for multiple comparisons and will be interpreted descriptively.

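### TRIM-D and EQ-5D are compared by a separate ANCOVA at every 8-monthly visit with no lead comparison, and later visits draw mainly on early recruits still on investigational product

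*Protocol*

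**What the plan says.** Section 2 lists "Patient reported outcomes from TRIM-D/EQ5D" among the secondary endpoints for metabolic management. The only patient-reported measure placed under the exploratory objectives is "Patient reported outcomes from study specific questionnaire".

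Section 6.3.1.1 describes TRIM-D as "scored to produce 5 sub-scale scores (Treatment Burden, Daily Life, Diabetes Management, Psychological Health, and Compliance) as well as a total score", which makes six scores. Section 8.3.6.5 summarises the total and each domain, then states "Score changes from baseline will be compared between treatments for each visit by an ANCOVA model". For EQ-5D, the five domains are only tabulated, but the utility score is tested: "Change from baseline will be compared between treatment groups for each visit by an ANCOVA model". Section 8.3.6.5 names no score or visit as the main one and leaves further detail to the analysis plan.

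On timing, Table 1 footnote 2 (Section 6) says "Assessments at month 8, 16, 24 etc. will include patient reported outcomes questionnaires", and the table adds the final visit. Table 2, for subjects who permanently stop investigational product, marks the questionnaires only at the clinic visit that follows discontinuation. The later 8-monthly clinic visits and the final visit have no entry. Section 6.3.1.1, by contrast, has all subjects completing TRIM-D at each 8-month visit and, as far as possible, at study completion or withdrawal.

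Section 8.3.6.2 analyses HbA1c, body weight and eGFR with a repeated mixed-effect model.

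**The concern.** There are two problems, both in what Section 8.3.6.5 fixes rather than in what it defers.

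First, a grid of score-by-visit tests with no lead cell can give different answers in different cells, such as the total against a domain or month 8 against a late visit. A reader can pick whichever one is nominally significant. Section 6.3.1.1 concedes that the minimal important difference for TRIM-D needs more work, so p-values may carry more of the interpretation than they should.

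Second, an ANCOVA run at one visit uses the subjects who have a score at that visit. In an event-driven trial with staggered entry, later visits are reached only by earlier recruits. If Table 2 is followed, subjects who have stopped product also drop out of those comparisons by design. The population compared therefore changes from visit to visit and drifts towards subjects still on product, and the two arms need not lose the same kind of subject.

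At stake is how the patient-reported result is read and reported. The MACE inference is not at stake.

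**Working it through.** **The plan's own figures.** The protocol states no power, alpha or error rate for TRIM-D or EQ-5D, so there is no figure on this point to reproduce. Its one design calculation reproduces: 4 x (1.960 + 1.282)^2 / (ln 1.3)^2 = 610.6, hence 611 events. That calculation concerns MACE only.

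**Number of tests.**
- Scores: TRIM-D total + 5 domains + EQ-5D utility = 7.
- Visits, long case: Table 3 gives total durations of 2.7 to 4.9 years. For the earliest recruits that is 32.4 to 58.8 months, or 4 to 7 visits at 8-month spacing.
- Visits, short case: Section 3.1 allows the study to end near the floor, "requiring that the projected median duration of subject follow-up be at least 1.5 years". With uniform recruitment over 1.5 years and a median of 1.5 years, the earliest recruits have 1.5 + 0.75 = 2.25 years (27 months), or 3 scheduled visits.
- Range: 7 x 3 = 21 to 7 x 7 = 49 tests.

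**Chance of at least one spurious result favouring albiglutide.** Assume no treatment effect, nominal two-sided 0.05 (so 0.025 in the favourable direction), and k test statistics with a common correlation rho. Then

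P = 1 - integral of phi(u) x [Phi((1.96 - sqrt(rho) u) / sqrt(1 - rho))]^k du.

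| Tests (k) | rho 0.3 | rho 0.5 | rho 0.8 |
|---|---|---|---|
| 1 | 2.5% | 2.5% | 2.5% |
| 21 | 28.8% | 21.6% | 11.4% |
| 28 | 33.8% | 24.7% | 12.5% |
| 49 | 44.2% | 31.3% | 14.9% |

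Counting a result in either direction, the rho 0.5 column becomes 43%, 49% and 62%.

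**Second correlation structure.** A simulation of 100,000 replicates built the TRIM-D total as the standardised sum of its domains, with separate correlations between scores and between visits. The chance of a favourable result was:

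| Correlation (scores/visits) | 3 visits | 4 visits | 7 visits |
|---|---|---|---|
| 0.3/0.5 | 28% | 33% | 44% |
| 0.5/0.5 | 23% | 28% | 38% |
| 0.7/0.7 | 16% | 19% | 24% |

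The size of the problem does not depend on the simpler model.

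**Who is in the later-visit comparisons.** Assume uniform recruitment over R years and a stop when the median is 1.5 years. Follow-up then runs from 1.5 - R/2 to 1.5 + R/2, and the share with less than 16 months (1.333 years) is 0.5 - 0.167/R. That is 39% for R = 1.5 and 44% for R = 3.0. In the Table 3 case with a 3.5% rate, 3.0-year recruitment and 3.4 years in total, follow-up runs from 0.4 to 3.4 years, and (1.333 - 0.4)/3.0 = 31% cannot reach month 16. Under Table 2, subjects who have permanently stopped product are removed on top of this. TRIM-D change scores are also unavailable for subjects on diet and exercise alone at baseline, who are exempt from the baseline TRIM-D.

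**The case against.** The strongest reply is that nothing confirmatory rests on these scores. Section 8.3.5 controls alpha only for MACE non-inferiority and then superiority, and Section 8.1 sets no patient-reported hypothesis. ANCOVA of change at a visit is a valid method. Section 8.3.6.5 leaves further detail to the analysis plan, which may name a lead score and visit and say how missing scores are handled. Section 6.3.1.2 also points readers to agreement between the two instruments rather than to one isolated result.

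Much of this stands. No trial-level type I error is affected, and the lead contrast could properly be named in the analysis plan. What it does not answer is that the protocol itself fixes a separate ANCOVA at each visit, and that Table 2 and Section 6.3.1.1 disagree on who is measured. Further detail in the analysis plan would add to that rule, not replace it.

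Two stronger readings are tempting. A reader might infer that a chance patient-reported benefit is likely. The figures do not support that. The rates near or above one half mostly count results in either direction. A favourable one passes 50% only with weakly correlated or independent tests over many visits (for example 51% at correlations of 0.3/0.3 over 7 visits). Independence is implausible, because the total is built from its domains and the same subjects return at each visit.

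A reader might also infer that these tests are meant as formal inference, because TRIM-D and EQ-5D are absent from the Section 8.3.5 list of secondary endpoints that "will not use any multiplicity adjustment procedure". But that list also omits secondary safety endpoints such as all-cause mortality, so it is not a complete register and absence from it proves little.

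**Conclusion.** The point holds as one about method and schedule. The per-visit ANCOVAs give a materially raised chance of a spurious favourable finding: about 22-31% at correlation 0.5 and 11-44% over 0.3 to 0.8, against 2.5% for one contrast. They also compare a changing and selected set of subjects at later visits.

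The percentages rest on assumptions the protocol does not supply: 3 to 7 visits, nominal two-sided 0.05, and the correlations. The 49-test case needs the slowest corner of Table 3. The share unable to reach month 16 assumes uniform recruitment. The disagreement between Table 2 and Section 6.3.1.1 rests on no assumption. No alpha-controlled conclusion changes.

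**What to change.** In Section 8.3.6.5, replace the per-visit ANCOVAs with one repeated-measures mixed model per score, with baseline, visit, treatment and treatment-by-visit terms, in line with Section 8.3.6.2. Take one lead contrast from it: the treatment difference in TRIM-D total averaged over months 8 and 16, estimated from the model using all available data. The same contrast for EQ-5D utility is supportive. The text should not say that nearly all subjects reach month 16. Report domains and other visits as nominal estimates with 95% CIs. Reconcile the questionnaire schedule in Table 2 with Section 6.3.1.1. Adding TRIM-D and EQ-5D to the Section 8.3.5 list would be a helpful label but would not be enough alone.

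The analysis change costs wording only and needs no new data. Reconciling the schedule would alter data collection only if questionnaires are to continue after discontinuation. The downsides are small: an isolated single-visit or single-domain difference could no longer be presented as the patient-reported result, and the mixed model still relies on scores being missing at random after discontinuation of product.

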9. STUDY CONDUCT CONSIDERATIONS

9.1. Posting of Information on Publicly Available Clinical Trial Registers

Study information from this protocol will be posted on publicly available clinical trial registers before enrolment of subjects begins.

9.2. Regulatory and Ethical Considerations, Including the Informed Consent Process

Prior to initiation of a site, GSK will obtain favourable opinion/approval from the appropriate regulatory agency to conduct the study in accordance with ICH Good Clinical Practice (GCP) and applicable country-specific regulatory requirements.

The study will be conducted in accordance with all applicable regulatory requirements, and with GSK policy.

The study will also be conducted in accordance with ICH E6 Good Clinical Practice (GCP), all applicable subject privacy requirements, and the guiding principles of the current version of the Declaration of Helsinki. This includes, but is not limited to, the following:

IRB/IEC review and favourable opinion/approval of the study protocol and amendments as applicable

Signed informed consent to be obtained for each subject before participation in the study (and for amendments as applicable)

Investigator reporting requirements (e.g. reporting of AEs/SAEs/protocol deviations to IRB/IEC)

GSK will provide full details of the above procedures, either verbally, in writing, or both.

Signed informed consent must be obtained for each subject prior to participation in the study

The IEC/IRB, and where applicable the regulatory authority, approve the clinical protocol and all optional assessments, including genetic research. Optional assessments (including those in a separate protocol and/or under separate informed consent) and the

clinical protocol should be concurrently submitted for approval unless regulation requires separate submission. Approval of the optional assessments may occur after approval is granted for the clinical protocol where required by regulatory authorities. In this situation, written approval of the clinical protocol should state that approval of optional assessments is being deferred and the study, with the exception of the optional assessments, can be initiated.

9.3. Quality Control (Study Monitoring)

In accordance with applicable regulations including GCP, and GSK procedures, GSK monitors will contact the site prior to the start of the study to review with the site staff the protocol, study requirements, and their responsibilities to satisfy regulatory, ethical, and GSK requirements.

When reviewing data collection procedures, the discussion will also include identification, agreement and documentation of data items for which the CRF will serve as the source document.

GSK will monitor the study to ensure that the:

Data are authentic, accurate, and complete.

Safety and rights of subjects are being protected.

Study is conducted in accordance with the currently approved protocol and any other study agreements, GCP, and all applicable regulatory requirements.

The investigator and the head of the medical institution (where applicable) agrees to allow the monitor direct access to all relevant documents.

